2.5.3 Predictive biomarkers

In case of any binary response defined a clinical endpoint, the predictive characteristics for each biomarker will be evaluated using a logistic regression model with the baseline biomarker and the response variable as binary outcome at Week 16. For the binary response at Week 16, a multivariate predictive panel will be identified used Elastic-net penalized logistic regression and the predictive value will be estimated as 10-fold cross-validated Area Under the ROC curve. These analyses will be computed for AD patients (lesional skin). Biomarkers will be ranked according to their importance in discriminating between responders and non-responders as

provided by RandomForest. A linear model will be used for change from baseline in clinical responses as continue parameters and baseline biomarker level.

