1.3 DETERMINATION OF SAMPLE SIZE

No formal sample size calculation was performed for this exploratory study. It was based on medical/clinical judgment and is consistent with the sample size from similar studies in the literature (2).

Allowing for drop-out rate of 15%, a total of approximately 24 pediatric patients with moderate-to-severe AD will be enrolled to achieve 20 evaluable patients. An approximately equal number of age, gender, location of targeted lesion area and site matched healthy volunteers serving as a reference comparator cohort will be enrolled. Any drop-out healthy volunteer for whom the matched patient is considered as evaluable will not be replaced.

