1.2 STUDY DESIGN

[figure not shown]
LPS16764 is a Phase 4 open-label, exploratory study in two sites evaluating the effect of dupilumab on skin barrier function in pediatric patients aged between ≥ 6 and < 12 years old with moderate-to-severe AD. A healthy volunteer cohort will be enrolled as a reference comparator matched to AD for age-, gender-, study-site and sampling will be matched on targeted lesion area. Approximately 24 pediatric patients with moderate-to-severe AD will be enrolled to achieve 20 evaluable patients. These enrolled AD patients will receive Investigational medicinal product (IMP) dupilumab treatment during the study. Approximately 24 healthy volunteers will be enrolled to achieve 20 evaluable subjects. These enrolled healthy volunteers will not receive any IMP treatment during the study.

The maximum study duration per participant will be 32 weeks. The study will comprise of:

- Screening period 1 (Day -28 to Day -1): Participants will be evaluated according to
- Inclusion and exclusion criteria.
- Baseline visit (Week 0, Day 1): Participants who remain eligible will be enrolled.
- A 16-week treatment phase for AD patients and a 16-week observation period for healthy volunteers.
- A 12-week follow-up period.

Biomarker assessment based on lipidomics, proteomics, and transcriptomics in STS samples will be conducted at baseline (Week 0, Day 1), Week 2, Week 4, Week 8, Week 12, EoT at Week 16, and Follow-ups at Week 22 and Week 28.

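### Biomarker SAP 2.5.3: in about 20 children, ordinary single-marker logistic regression gives no usable odds ratio, and a misleading default p-value, for the markers that best separate responders (minor)

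*SAP*

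**What the plan says.** Biomarker SAP 2.5.3 opens with a condition, "In case of any binary response defined a clinical endpoint", and then states that the "predictive characteristics for each biomarker will be evaluated using a logistic regression model with the baseline biomarker and the response variable" taken as a binary outcome at Week 16. The work is limited to lesional skin of AD patients. No penalty, exact method, test statistic, p-value threshold or rule for non-convergence is given for these one-marker models.

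The same section plans three other analyses:

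- For the binary response, "a multivariate predictive panel will be identified used Elastic-net penalized logistic regression", with a cross-validated area under the ROC curve.
- "Biomarkers will be ranked according to their importance in discriminating between responders and non-responders", by RandomForest.
- For continuous responses, "A linear model will be used for change from baseline in clinical responses".

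The penalty is attached to the panel only, so the one-marker model reads as ordinary maximum likelihood. On numbers, Biomarker SAP 1.2 states: "Approximately 24 pediatric patients with moderate-to-severe AD will be enrolled to achieve 20 evaluable patients". Section 2.6 calls all analyses exploratory and rules out formal hypothesis testing. Section 3 names R 4.0.0.

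**The concern.** Maximum-likelihood logistic regression has no finite slope when a cut-point on the marker divides responders from non-responders without overlap. The fitting routine stops at an arbitrary large slope with an enormous standard error. The Wald p-value, which R's standard logistic summary prints, is then close to 1. Short of complete separation, the standard error can still grow faster than the slope, so a better marker can receive a worse Wald p-value.

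With about 20 children this is not a rare accident for a strong marker. The section exists to find baseline predictors of response to dupilumab. For a binary response, the one-marker logistic model is the only planned analysis that yields an odds ratio and interval for each marker. It would supply neither in usable form for the markers of most interest.

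**Working it through.** **Inputs.**

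- Evaluable AD children: 20, from 24 enrolled (Biomarker SAP 1.2; clinical SAP 1.3).
- Responder split: not given, because neither SAP defines a binary response. Assumed 14/6, with 10/10 and 16/4 as a range.
- Marker: assumed normal in each response group, with the means differing by d standard deviations.

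**The plan's own figure.** Inflating 20 for 15% drop-out gives 20 / 0.85 = 23.5, rounded up to 24. This matches.

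**Scale.** For a normal marker, true AUC = Φ(d/√2). So d = 1.5, 2, 2.5 and 3 correspond to AUC of about 0.86, 0.92, 0.96 and 0.98.

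**Step 1: one separated data set, 14/6.** R's standard logistic fit (checked in version 4.3.3) gave slope 206, standard error about 139,000 and Wald p = 0.999, with non-convergence warnings. Two other statistics for the same data can be done by hand:

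- Likelihood ratio. The fitted log-likelihood tends to 0, so the statistic is 2 × (20 ln 20 − 14 ln 14 − 6 ln 6) = 2 × (59.91 − 36.95 − 10.75) ≈ 24.4 on 1 df, p ≈ 7.7 × 10⁻⁷.
- Exact rank test. p = 2 / C(20,6) = 2 / 38,760 ≈ 5.2 × 10⁻⁵.

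Firth regression on separated 14/6 samples gives a finite slope, with median p about 0.00003 to 0.0001.

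**Step 2: how often, at 14/6.** Share of simulated trials:

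| Difference (SD) | Wald p<0.05 | Firth p<0.05 | Complete separation |
|---|---|---|---|
| 1.5 | 52% | 81% | not tabulated |
| 2 | 56% | 98% | 11% |
| 2.5 | 38% | 100% | 29% |
| 3 | 19% | 100% | 52% |

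Repeat simulations of 1,500 trials per cell put the Wald column at 48–52%, 53–55%, 34–35% and 17–18%, so the pattern is stable to a few points.

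**Step 3: other splits.** Wald p<0.05 at 1.5, 2, 2.5 and 3 SD:

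- 10/10: 70%, 68%, 46%, 21%. Exact Mann-Whitney: 86%, 98%, about 100%, 100%.
- 16/4: 20%, 22%, 16%, 10%. Exact Mann-Whitney: 69%, 91%, 97%, about 100%.

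**Step 4: near-separation alone.** Excluding completely separated samples, at true AUC 0.98 the Wald p was below 0.05 in 45% (10/10), 41% (14/6) and 23% (16/4). The likelihood-ratio test reached that level in about 100%.

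**Step 5: type I error at 14/6, no true difference.** Wald 2%, likelihood ratio 8% (5 to 7.5% across splits in a repeat run), Firth 4.5%.

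**The case against.** A reader might infer that the strongest markers are lost, or ranked below mediocre ones. The plan does not support that. Section 2.5.3 assigns the ranking to RandomForest and the panel to a penalised model, and neither breaks down under separation. The linear model for continuous responses is unaffected too.

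A reader might also infer that a Wald screen at 5%, or at a stricter cut-off across many genes, is planned. It is not. No test statistic or threshold is named, and section 2.6 disclaims formal testing. The Wald percentages describe what the default software output would show, not a decision rule in the plan. A likelihood-ratio p-value from the same fit would still detect the marker. If predictive characteristics were read as discrimination, the AUC of a one-marker logistic model equals that of the marker, so a separating marker would come first. R also warns when the fit fails, so the failure is not silent.

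Three further limits stand:

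- Complete separation is the exception below about 3 SD (5 to 13% at true AUC 0.90, depending on the split), and nothing in the documents says that markers this strong exist.
- The analysis may never run, because no binary response is defined and the primary endpoint is a continuous percent change.
- A separated marker need not be a true predictor. At 16/4 a null marker separates with probability 2 / C(20,4) = 2 / 4,845 ≈ 0.0004, or about 6 of an assumed 15,000 genes. Firth regression does not remove that.

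These points remove any claim about lost or misranked markers. They do not rescue the estimate: the maximum-likelihood odds ratio under separation is infinite whichever test is used. Where no testing is intended, the estimate and its interval are what the reader is left with.

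**Conclusion.** The point holds for the single-marker logistic output only. If a binary response is defined, the stated method will give no usable odds ratio or interval for markers that separate the groups, and very unstable ones near separation. The p-value printed by default will mislead in the same cases. The size rests on an assumed normal marker, 20 children and an assumed responder split; the direction was the same at all three splits examined.

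Severity is minor. The analysis is exploratory and conditional, and other planned methods cover ranking and the multivariable panel. It is still more than missing detail, because the method as written fails in a foreseeable way at this sample size and a better one is readily available.

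**What to change.** In Biomarker SAP 2.5.3, state that the single-marker models for a binary response are fitted by Firth penalised-likelihood logistic regression, reporting odds ratios with profile penalised-likelihood confidence intervals and p-values. Keep the RandomForest ranking, the elastic-net panel and the linear model as planned.

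The cost is one sentence and a different R function; no new data are needed. The downside is that odds ratios are shrunk slightly towards 1. Switching only to a likelihood-ratio p-value would be a partial repair, since the odds ratio would stay infinite under separation.

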4.3.3 Analyses of evaluation variables

4.3.3.1 *Analysis of main evaluation variable(s)*

The primary endpoint will be analyzed on the mITT population. As a sensitivity analysis, it will also be analyzed based on the ITT population.

The calculation of changes (absolute and percent) from baseline will be based on the same number of STS (ie, for absolute change from baseline after 5 STS at W16: Change TEWL at W16 after 5 STS = TEWL value at W16 after 5 STS – TEWL value at baseline after 5 STS).

If a change in spot anatomical location changed versus Day 1 is identified and assessed by the study team as having a significant impact on skin barrier, only visits prior to the location change will be considered in the statistical analysis of TEWL data. Raw data and change (absolute and percent) from baseline will be summarized with descriptive statistics by timepoint.

Profiles over time (from baseline to Week 16) will be generated for individual values (spaghetti plot).

For information purpose as study is not powered (no multiplicity correction will be applied):

- For each number of STS, the evolution of the percent change from baseline over time will be analyzed using a repeated measures analysis of variance with visit, type of skin, interaction between visit and type of skin, age, and baseline value as fixed effects and subject identifier as random effect, at a Type 1 error level of alpha=0.05. In case of heterogeneity at baseline, additional covariates (ie, site, race ...) could be added in this statistical model.
- The following covariance structures will be tested in the REPEATED statement of the PROC MIXED: un, vc and cs at least. The structure with the smallest Bayesian information criteria will be selected for the final model.
- Point estimate and two-sided 95% confidence interval and corresponding two-sided p-value will be reported for each effect. No comparison will be performed.
- If assumption of normal distribution is strongly violated, transformation method could be used: eg, log transformation; normality assumption will be assessed through quantile-quantile plot and Shapiro-Wilk test at 5% Type I error.

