2.4 CORRELATION ANALYSIS

2.4.1 Correlation between biomarker and TEWL

In addition to the correlation analysis between each the composite biomarkers and the TEWL, the association between each single biomarker (lipidomics, proteomics, transcriptomics) and TEWL will be investigated at baseline in a linear model adjusted for the study group and age. TEWL at baseline will be evaluated as TEWL. Biomarker will be ranked according to their importance in explaining TEWL using RandomForest for regression. The Correlation between change in biomarker and change in TEWL, the correlation between baseline biomarker and change in TEWL will be investigated.

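### The linear model for change in biomarker SAP 2.5.3, and the correlation with change in TEWL in 2.4.1, omit the outcome's baseline value, so a marker that only tracks baseline severity can look predictive

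*SAP*

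**What the plan says.** Biomarker SAP 2.5.3 (Predictive biomarkers) has two parts. Most of it concerns a binary response: each marker is assessed "using a logistic regression model with the baseline biomarker and the response variable as binary outcome at Week 16", followed by an elastic-net panel and a random-forest ranking. Its last sentence covers continuous outcomes: "A linear model will be used for change from baseline in clinical responses as continue parameters and baseline biomarker level". That sentence names one predictor.

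Biomarker SAP 2.4.1 adds that "the correlation between baseline biomarker and change in TEWL will be investigated", again with no adjustment named.

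No section of the biomarker SAP adds the outcome's baseline value to either analysis. Covariates are named elsewhere. The cross-sectional model of baseline TEWL in 2.4.1 is fitted "in a linear model adjusted for the study group and age". The clinical SAP (4.3.3.1) models percent change in TEWL with "age, and baseline value as fixed effects and subject identifier as random effect". Biomarker SAP 1.3.3 defines the endpoints as both percent and absolute change, and 2.6 calls all the biomarker work exploratory, without formal hypothesis testing.

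**The concern.** Change is the follow-up value minus the baseline value, so it is normally correlated with baseline. Two mechanisms produce this: regression to the mean, and a treatment effect that is larger in children who start worse. A marker that tracks baseline severity inherits a correlation with change even if it says nothing further about who responds. Correlation with severity is to be expected here: 2.4.1 and 2.4.2 plan to look for it, and the tape strips come from the same procedure at which TEWL is measured (1.7.1).

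At stake is the content of the list of predictive markers. Severity markers can rise in it, while a marker that acts independently of severity is tested against residual variance that baseline would have explained. Every AD patient receives dupilumab, so no untreated AD arm would expose severity-driven associations.

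**Working it through.** **Inputs from the documents.** The clinical SAP (1.3) states that approximately 24 patients "will be enrolled to achieve 20 evaluable patients", allowing 15% drop-out. Check: 20 / (1 - 0.15) = 23.5, rounded up to 24, which reproduces the plan's figure. The calculations use n = 20.

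**Assumed inputs.** The documents give no correlations, reliabilities or variances. Let q be the correlation of marker and baseline outcome, r the correlation of baseline and Week 16 outcome, and k the Week 16 SD divided by the baseline SD. The biomarker SAP sets no alpha; two-sided 0.05 serves only as a yardstick.

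**Step 1: coupling of change with baseline.**

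corr(baseline, change) = (rk - 1) / sqrt(k² + 1 - 2rk)

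- With k = 1 this is -sqrt((1 - r)/2). At r = 0.5 it is -sqrt(0.25) = -0.50.
- With k = 1, a value of -0.7 would need r = 1 - 2(0.49) = 0.02. In practice -0.7 therefore implies that variance falls on treatment. For example, r = 0.5 and k = 0.7 give -0.65 / sqrt(0.79) = -0.73.

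For a marker that adds nothing once the observed baseline is known, corr(marker, change) = q × corr(baseline, change). With q = 0.5 and -0.50 this is -0.25.

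**Step 2: simulated rejection rates, marker adding nothing beyond the observed baseline (n = 20).**

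| Setting | Unadjusted | Baseline added |
|---|---|---|
| k = 1, r = 0.5, q = 0.3 | 9.6% | about 5% |
| k = 1, r = 0.5, q = 0.5 | 18.2% | about 5% |
| k = 1, r = 0.5, q = 0.7 | 33.4% | about 5% |
| corr(change, baseline) = -0.7, q = 0.5 | about 33% | about 5% |
| k = 0.5, r = 0.5, q = 0.5 | about 50% | about 5% |
| q = 0 | about 5% | about 5% |

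Over r and q from 0.3 to 0.7 with k = 1, the unadjusted range is 7.7% to 46.3%.

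**Step 3: power.** Take a marker uncorrelated with baseline, correlated 0.5 with change, and corr(change, baseline) = -0.7. Power is about 64% unadjusted and about 95% adjusted.

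**Step 4: the marker tracks true severity and the score has measurement error.** Write true severity as T. The observed baseline is T plus error, and Week 16 is b × T plus new error.

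- b = 1 (pure regression to the mean), test-retest 0.5, q = 0.3 / 0.5 / 0.7: the unadjusted model rejects 5% / 5% / 5%, the adjusted one 11% / 29% / 75%. At test-retest 0.7 the adjusted rates are 8% / 17% / 43%. Change is then only a difference of two errors, which the marker does not share. Conditioning on a noisy baseline creates the association.
- b = 0.25 to 0.5 (treatment shrinks severity), reliability 0.5 to 0.9, q = 0.3 to 0.7: about 9% to 88% unadjusted, about 5% to 28% adjusted.

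**Step 5: percent change (n = 20).** If Week 16 is proportional to baseline (log-slope 1), the unadjusted rate is about 5% and the problem vanishes. For log-slopes 0.7 to 0.3 and q = 0.5 to 0.7 it is 12.9% to 58.3%, against about 5% adjusted.

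**The case against.** The strongest objection is that baseline adjustment is not a general remedy. Step 4 with b = 1 bears this out: there the plan's unadjusted model is correct and the adjusted one misleads. Marker and TEWL share a procedure, so their errors may be correlated, but that argument does not extend to EASI, POEM, CDLQI or the NRS scales. This stands as a caveat. It does not reverse the point, because it requires a treatment that leaves differences in true severity unchanged. On an active drug, shrinkage of severity is the more plausible case, and there adjustment generally does better.

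A second objection is that a severity marker does predict change in the marginal sense, and 2.5.3 does not claim independence from severity. That is fair. The unadjusted association answers a legitimate question and should stay, but it does not show what a marker adds to a baseline score already in hand.

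A third is that the work is exploratory with no formal testing. This limits the harm to ranking and interpretation. It does not remove the bias, which is systematic and would survive any multiplicity correction. The contrast with the clinical SAP model is suggestive only, since that model serves another question.

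A reader might infer that all the models in 2.5.3 share the defect. The text does not support that: the logistic, elastic-net and random-forest analyses use a binary Week 16 response, left undefined, and do not model change. Nor does it support saying that severity markers will be reported as predictive. They can be, if they correlate with baseline.

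**Conclusion.** The point holds for two analyses: the linear model closing 2.5.3 and the correlation of baseline biomarker with change in TEWL in 2.4.1. As written, neither separates prediction of response from tracking of baseline severity.

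The bias can be substantial at n = 20: about 18% to 33% against a nominal 5% in the central settings (q = 0.5, change-baseline correlation -0.5 to -0.7), the upper figure requiring variance to fall on treatment. It is absent when the marker is unrelated to baseline, when percent change is used and Week 16 is proportional to baseline, or when change is pure measurement error and the marker tracks true severity. All these rates rest on assumed correlations. The consequence is misleading exploratory ranking and interpretation, with no effect on a confirmatory error rate. The change is worth making because it is cheap.

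**What to change.** - In biomarker SAP 2.5.3, fit change = baseline value of that endpoint + baseline biomarker.
- In 2.4.1, give the partial correlation of baseline biomarker with change in TEWL, adjusted for baseline TEWL at the same strip count and skin area.
- Present these as the main result for what a marker adds beyond severity, with the unadjusted association alongside.
- State that error in the baseline score can bias the adjusted estimate, so a disagreement between the two results needs interpretation.
- Describe findings as *associated with outcome on dupilumab*, since every AD patient is treated.

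The cost is SAP wording, one degree of freedom per model and one extra column of output. The baseline values are already collected.

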2.6 MULTIPLICITY ISSUE

All analyses will be exploratory. No formal hypothesis testing will be conducted.

2.7 BIOINFORMATICS METHODS AND RESULTS INTERPRETATION

2.7.1 Analyses based on biomarkers regulated by treatment from longitudinal analysis of RNA-seq

- Downstream effect analyses (GO terms, biological processes and diseases) of regulated gene sets in Ingenuity Pathway Analysis (IPA) to get mechanistic insights into disease-affected biological processes.
- Pathway Enrichment Analyses (Over-representation analysis, t-test based) aimed to the identification of curated biological pathways involved in regulated gene patterns (MetaCore [Clarivate Analytics], IPA Core Analyses [Qiagen])

2.7.2 Functional protein association networks

For identifying proteins sets, functional protein association networks will be built and interpreted using the String database.

3 SOFTWARE DOCUMENTATION

All analyses of clinical data will be performed under the responsibility of Sanofi Biostatistics Department using R software Version 4.0.0 ([2](#)).

4 SUPPLEMENTARY INFORMATION

4.1 DETAILED BIOMARKER ASSESSMENTS

4.1.1 Lipidomics

Skin lipidomics samples may be stored for a maximum of 5 years following the last participant's last visit in the study at a facility selected by the Sponsor. Detailed guidelines and requirements for samples preparation, handling of skin tapes after stripping, and storage and shipment of such skin tapes will be provided in the study reference manual.

4.1.1.1 *Filaggrin breakdown products*

Filaggrin is a structural protein that plays an important role in controlling water retention in the skin, and the hygroscopic properties of FLG breakdown products have an important role as natural moisturizing factor ingredients. Filaggrin deficiency leads to impaired lipid profile and altered acidification pathways. Lipid abnormalities have been reported in patients with FLG mutations. Filaggrin breakdown products, cis/trans-urocanic acid (total UCA) and pyrrolidone carboxylic acid (PCA), also known as pyroglutamic acid, will be quantified via a liquid chromatography electrospray ionization tandem mass spectrometry (LC-ESI-MS/MS) approach in the same tape strips that are used for lipidomics assessment.

4.1.1.2 *Analysis of stratum corneum lipids*

It has been reported that lesional and non-lesional skin of AD patients has decreased EOS CER and other CER with very long-chain fatty acids (C22-C30) and increased short-chain fatty acids NS CER (C16-C22). Highly hydrophobic omega-esterified acid sphingosine CER (EOS CER) and NS CER will be analyzed as follows.

STS processing for lipid extraction

STS will be processed through a Bligh and Dyer procedure. The bottom chloroform layer from the skin tape extraction will be used for lipid analyses while upper water-methanol phase will be used for polar component analyses by the Liquid Chromatography with tandem Mass Spectrometry (LC-MS/MS). All mass spectrometric data will be normalized to the total amount of hydrolyzed protein determined. EOS CER and NS CER will be identified and quantified using a targeted ultra-high performance liquid chromatography electrospray ionization tandem mass spectrometry (UHPLC-ESI-MS/MS).

4.1.1.3 *Quantification of protein bound ceramides*

Protein bound ceramides are formed from EOS CER and represent a portion of EOS CER without linoleic acid, thus having a terminal hydroxyl group N-linked fatty acid. Protein-bound ceramides

are released from proteins during protein hydrolysis. After protein determination in hydrolysates, freed omega-OH CER will be extracted and omega hydroxy fatty acid containing CER will be detected by the UHPLC-ESI-MS/MS. Values obtained will be normalized against protein content in the samples.

